## **D. Research Design and Methods**

[figure not shown]
### **1. Overview**

It is likely that irritable bowel syndrome (IBS) is the result of multiple disease mechanisms which lead to the expression of a common set of symptoms. The goal of this proposal is to identify and characterize a more homogeneous subset of IBS patients—specifically, IBS patients with comorbid somatization (IBS-S). I will define the IBS-S subgroup by their CNS responses within the homeostatic afferent processing network (HAPN), regions important to the higher level (cognitive and affective) responses to pain. *The overarching hypothesis of these investigations is that aberrant central pain responses within the HAPN result in somatization pain symptoms, and as such may have pathophysiologic relevance to the bowel pain experiences of the IBS-S subgroup.* Building upon my initial observations that IBS-S subjects demonstrate greater HAPN activations to visceral stimuli, Specific Aim 1 will examine whether these responses generalize to non-visceral (somatic) stimuli. Given treatment refractoriness to antidepressants in IBS-S subjects, and the known influence of these medications on the HAPN, Specific Aim 2 will assess the effect antidepressant therapies on IBS-S central pain activation patterns. Ultimately, this work will provide greater insight into the neuropathophysiologic basis of IBS-S, allowing for the objectively definition of IBS-S as an important irritable bowel subgroup.

**Specific Aim 1. To compare HAPN activations following noxious somatic stimulation in IBS subjects based on the presence of somatization.**

Rationale: It has been demonstrated that CNS responses to noxious visceral stimulation differ within the HAPN from healthy controls subjects in some, but not all, IBS subjects. My preliminary data supports the hypothesis that IBS subjects with comorbid somatization (IBS-S) demonstrate a pattern of greater CNS activation within the homeostatic processing afferent network (HAPN) following visceral stimulation compared to those with no somatization (IBS-No S). Specifically, the regions responsible for higher-level cognitive (bilateral orbitofrontal, right prefrontal cortex) and affective (right insula, bilateral anterior cingulate cortex) pain processing had greater activations in IBS-S subjects. Given that IBS-S subjects experience multiple somatic pain symptoms, in this Aim I will determine whether the previous difference in HAPN pain responses in the two IBS populations (IBS-S and IBS-No S) is specific to visceral stimuli, or is a more generalized pain response which can also be elicited by somatic stimulation.

Design and Methods: HAPN responses to both visceral and somatic stimuli will be evaluated in 40 female IBS patients stratified by the presence of somatization (20 IBS-S and 20 age-matched IBS-No S subjects) and 20 healthy controls. Measures of current IBS symptoms and concurrent mood symptoms will be assessed as potential confounders using self-report instruments and structured psychiatric interviews (see “Assessment

**Figure 8. Overview of study design for Specific Aim 1.** Female IBS subjects with somatization (IBS-S) and without somatization (IBS-No S) and healthy controls will undergo a series of four functional magnetic resonance (fMRI) blocks, each assessing brain activations in response to randomized visceral and somatic stimuli. Between-group (IBS-S vs IBS-No S) differences in brain activations within the homeostatic afferent processing network (HAPN) in response to these stimuli will then be evaluated.

measures", below).

All three subject groups will undergo a baseline functional MRI study of 4 functional imaging blocks obtained during a protocol of randomized visceral (25- and 50-mm Hg rectal balloon distensions) and somatic stimuli (1.4 kg-cm^2 nailbed pressure) (Figure 8, above). The primary endpoint of interest is differences in CNS activations of *a priori* regions of interest comprising the HAPN following somatic stimulation.

Analysis/interpretation: As a result of a more generalized abnormal pain response within the HAPN, it is hypothesized that IBS-S subjects will demonstrate greater activations of the HAPN with noxious somatic stimuli, compared to IBS no-S subjects and healthy controls. This hypothesis thus predicts a "IBS Group x Somatic stimulus" effect on two-way ANOVA analysis of activations within *a priori* HAPN regions. Specifically, it is hypothesized that the significantly increased HAPN activation pattern observed in IBS-S subjects compared to IBS-No S subjects that was observed following noxious visceral stimulation (preliminary data) will be present following noxious somatic stimulation in the IBS-S subjects, but not in the IBS-No S or healthy control groups (Figure 10, below). If this HAPN activation response to somatic stimuli is indeed observed in IBS-S subjects, it would support my hypothesis that in IBS-S patients, the presence of somatization reflects a less discriminate HAPN response to noxious stimuli, which includes not only visceral, but also somatic stimuli. This global overactivation of the HAPN in IBS-S subjects thus could have mechanistic relevance to the multiple pain experiences in affected individuals.

Alternately, if HAPN activation differences in IBS-S subjects are found only to be specific to visceral stimulation, the possibility that the HAPN is relevant to visceral, but not somatic, pain experiences in IBS-S subjects would be considered. This would imply that several distinct, system-specific sensory defects (i.e., gut, musculoskeletal, etc.) may be present in somatization, rather than the global pain processing abnormality within the HAPN as is hypothesized to be relevant to the multiple pain experiences of IBS-S subjects.

If greater HAPN activations are detected in both IBS-S and IBS-No S subgroups, this would be interpreted as possibly indicating that somatic afferent sensory signals are more potent activators of the HAPN than are visceral afferent signals, resulting in HAPN activation patterns with noxious somatic stimulation which are indistinguishable in the two IBS groups. This conclusion might be valid particularly if the difference in visceral pain responses seen in the preliminary data are again observed in this IBS cohort. It would thus still be conceivable that differences in HAPN somatic responses could be detected in future studies which implement either less intense somatic stimuli (i.e., lower level thumb pressures) or alternative somatic stimuli (thermal stimuli).

[figure not shown]
Pitfalls/Limitations: Critical to the study is an accurate determination of study group assignment (IBS-S or IBS-No S) and the limitation of potential confounders. Thus, substantial effort will go into the determination of somatization status, including the use of validated self-report instruments (PHQ-15), medical chart review and history by the investigator, and a formal structured interview (C-DIS). Other potentially important confounders will also be considered. To address differences in brain activations due to handedness, gender, and age, subjects will be age-matched within 5 years, and only will be right-handed females will be studied. Subjects with major depression, anxiety, or current antidepressant use will also be excluded. Current depression, anxiety, and duration and severity of bowel symptoms will also be assessed using both validated self-report and standardized interviews. Additional ANOVA models will be run to confirm that HAPN activation differences attributed to somatization are not accounted for by other IBS disease factors (duration, symptom severity) or psychological features are also relevant to observed differences in brain activation. Subject movement during the fMRI study is also a consideration given the noxious nature of the study stimulus. Preliminary data acquired using a similar protocol did not suggest this to be a major issue, either in terms of subjective reports of discomfort or on assessment of movement during quality-control assessments. No subjects withdrew from the preliminary study due to protocol intolerance. However, if movement is introduced as a problem in this investigation, it is anticipated that it will be increasingly present in the latter blocks of the protocol (i.e., fMRI blocks 3 and 4). The proposed block design of the proposed fMRI study allows for the exclusion of study blocks demonstrating excessive subject movement. Study recruitment may present a potential pitfall, though in the past I have been successful in meeting recruitment goals through my outpatient practice given my clinical emphasis on IBS and related functional GI disorders. If recruitment does prove to be an issue, recruitment efforts will be expanded to

include the Washington University Volunteers for Health database and the use of recruitment advertisements on the WU Medical Center campus.

**Specific Aim 2. To compare the effects of antidepressant therapy HAPN activations following noxious visceral stimulation in IBS subjects based on the presence of somatization.**

Rationale: Case-control and randomized clinical trial data have established that somatization predicts symptom responses to IBS therapy with the tricyclic antidepressant desipramine. Specifically, IBS-S subjects are more refractory to antidepressant therapies, while IBS-No S subjects have better overall responses to the same treatment. A recent study has demonstrated improvements in HAPN visceral activations (anterior cingulate cortex) following desipramine therapy in an IBS cohort. Given these observations, the goal of this Aim is to assess whether differences in visceral HAPN activation patterns following desipramine treatment can be detected in IBS-S and IBS-No S subjects.

Design and Methods: The proposed study implements open-label desipramine therapy in 40 IBS (20 IBS-S and 20 age-matched IBS-No S) subjects. Participants from Aim 1 will be invited to continue on to open-label therapy in Aim 2. IBS-S and IBS-No S subjects will receive a 4-week treatment course with the tricyclic antidepressant desipramine (DES), as detailed in section 2.D., below. Subjects will undergo a fMRI protocol with noxious visceral and somatic stimuli as in Aim 1 at baseline, and then immediately following the 4-week desipramine therapy. Subjects will undergo baseline, and post-therapy assessment of psychiatric comorbidity (depression/anxiety) and IBS symptom severity (as described in 3.A. and 3.B., below). The primary endpoint is differences in visceral stimulation-induced brain activations of the HAPN on fMRI, ascertained between-groups following desipramine therapy. The proposed study design is outlined in Figure 9.

[figure not shown]
**Figure 9. Overview of study design for Specific Aim 2.** IBS patients with somatization (IBS-S) and without somatization (IBS-No S) will be identified. A baseline fMRI protocol (as in Aim 1) will be obtained at baseline, followed by a 4-week, open-label treatment with desipramine. A second fMRI protocol will be performed post-desipramine therapy at week 4. The primary endpoint of interest is post-treatment differences in visceral HAPN activations between IBS-S and IBS-No S subjects.

Analysis/interpretation: *Consistent with the clinical refractoriness to antidepressant therapy observed in IBS-S subjects, it is hypothesized that IBS-S subjects will exhibit a persistent pattern of abnormal HAPN activations in response to visceral stimulation following desipramine therapy.* By comparison, it is hypothesized that the IBS-No S group will exhibit decreases in HAPN activations in the post-treatment fMRI protocol (Figure 10, below). Region of interest two-way ANOVA models will be developed in comparing  $\Delta$ baseline-DES activations, with IBS Group (IBS-S and IBS-No S) as a between-subject factor. If the stated hypothesis is supported by the fMRI findings, it would suggest that the persistent HAPN activations in response to visceral afferent signals may result in the less robust clinical responses to desipramine therapy in the IBS-S. This finding would be an important addition to the existing literature, providing both insight into the central mechanisms involved in IBS antidepressant response, and also into the specific relevance of HAPN pain responses to the IBS-S subgroup.

Conversely, should HAPN activations be found to improve in both IBS groups following desipramine therapy, the possibility that HAPN visceral activations are indeed partially refractory to desipramine in IBS-S, but the detected between-group differences (IBS-S vs. IBS-No S) in post-desipramine changes in HAPN activation were smaller than expected, and thus not statistically significant. If this were the case, the ANOVA analyses would be likely demonstrate statistical trends between the IBS groups, and enrollment of additional subjects would be considered if feasible following power calculations. This additional step might lead to findings which allow for rejection of the null hypothesis.

[figure not shown]
**Pitfalls/Limitations:** Pitfalls and limitations as described in Aim 1 are also applicable to this Aim, and will be addressed as outlined previously. Also a consideration is the use of repeated fMRI measures within the same individual, and the influence that previous experiences will have on subsequent fMRI studies (e.g., anticipation). Theoretically this effect should be distributed across treatments and IBS study groups equally, such that the anticipated effect, if any, bias towards the null. Existing literature discussing this phenomenon suggests that the proposed regionwise analyses based in *a priori* hypotheses are more immune to this phenomenon. This study is proposed without a placebo control arm. This design was decided upon after discussion with my mentors in order to facilitate subject recruitment and protocol adherence. While an obvious limitation of the study design, given previous data that demonstrates the effects of tricyclic medications over placebo within the HAPN, foregoing a placebo-controlled arm was felt to be a reasonable approach.

The observed changes HAPN activation seen following desipramine therapy in this Aim likely represent the direct effects of desipramine on these brain regions. This conclusion can be deduced from previous pharmacoradiologic and animal model studies demonstrating the actions of tricyclic antidepressants in these regions. The possibility remains, however, the desipramine is influencing the CNS proximal to the HAPN (i.e., at the level of the viscera, spinal cord, or brainstem), in turn decreasing HAPN activations via a reduction in visceral afferent signals. This possibility can be reconciled in future analyses which examine the data generated by this Aim, utilizing sophisticated functional connectivity models to establish the temporal relationships of these regional activations.

**Figure 10. Summary of the anticipated findings in Specific Aims.** It is hypothesized that IBS-S subjects will demonstrate greater HAPN activations with noxious somatic stimuli, compared to IBS subjects with no somatization (IBS-S) and healthy controls (Specific Aim 1). It is also anticipated that IBS-S subjects will demonstrate a persistent pattern of abnormal HAPN visceral activations following desipramine therapy, whereas significant improvements in HAPN visceral activations will be observed in IBS subjects with no somatization following antidepressant therapy (Specific Aim 2). n/a=not assessed--control subjects do not participate in treatment arm of Specific Aim 2.

This study is proposed without a placebo control arm. This design was decided upon after discussion with my mentors in order to facilitate subject recruitment and protocol adherence. While an obvious limitation of the study design, given previous data that demonstrates the effects of tricyclic medications over placebo within the HAPN, foregoing a placebo-controlled arm was felt to be a reasonable approach.

**Future directions.** Recent epidemiologic studies have demonstrated greater prevalence of functional genetic polymorphisms of monoaminergic neurotransmission, including the serotonin transport protein (SERT), in IBS compared to healthy controls. Neurophysiologic studies in animal models and mood disorders have identified serotonin as important to nerve signaling within the HAPN. In future studies, I will attempt to link established serotonergic genetic polymorphisms (such as SERT) to the presence of CNS activation patterns in IBS subjects. Studies to-date evaluating the genetic basis of IBS have evaluated IBS subjects as a single group. The presumed heterogeneity in IBS pathophysiology has driven the need for large samples of several hundred individuals to ascertain even weak

associations in previous IBS genetic studies (Figure 11A). These observations emphasize the need for the rational dissection of IBS into more discrete, homogeneous “endophenotypes”—intermediate phenotypes that help establish the causal link between genes and overt symptom expression. The assumption of the endophenotype is that it represents a more homogeneous population, and thus one which is more likely to be impacted by a particular system defect, and in turn a more specific set of genes (Figure 11B). Identification of mechanistically relevant IBS endophenotypes has been endorsed as a way forward in understanding the genetic basis of IBS and related somatization disorders. The IBS-somatization (IBS-S) endophenotype is an example of such an IBS subset. IBS-S subjects can be identified on the basis of patient history and questionnaires, but also have a distinct clinical phenotype (e.g., more severe symptoms, multiple pain syndromes, treatment refractoriness) and are also associated with an objective measure (brain HAPN responses to noxious stimulation). Applying these objective filters over subjective symptom reporting alone, described functional genetic polymorphisms have the potential to yield much more robust impact on the syndrome.

Functional neuroimaging techniques, in which substantial data sets are acquired from a single subjects from hundreds of repeated measures of brain function, is a powerful tool when coupled with genetics. This is the

concept of “*imaging genomics*”, in which signal detection power allows for the study of tens, rather than hundreds of subjects in making significant gene-brain activation associations. This technique has been applied successfully in other similar conditions, including a recent National Institute of Mental Health study of 14 depressed subjects found that those carrying the

**Figure 11. Strategies for the future study of genetics in irritable bowel syndrome.** Gene-to-disorder approaches (A) have relied on self-report of symptoms in identifying study subjects with IBS, and assume direct linear relationships between genes and IBS. (B) By interposing objective measures (e.g., more specific symptom subsets, differences in fMRI findings), an intermediate IBS “endophenotype” may be identified, potentially bridging the gap between single gene effects and the clinical phenotype.

SERT promoter s allele were found to have hyper-reactive responses of their amygdala to stressful environmental stimuli. Genetic factors, particularly relating to candidate neurotransmitter systems, present an appealing area for future pursuit of a biological basis for irritable bowel in the IBS-S endophenotype. In preparing for the application of these techniques in future investigations, I have enlisted [name] as a consultant and advisor, and will integrate formal and practical genetics training opportunities into my career development plan.

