## Findings

**Clinical features and subjective pain ratings:** 24 right-handed female subjects (8 in each study group) underwent fMRI during the rectal balloon distention protocol from April 2007 to June 2008. A summary of the clinical features and subjective pain ratings in response to the balloon distentions are reported in Table xx. Subject ages were not significantly different across study groups. However, there were significant differences in IBS symptom ratings between the IBS-S and IBS-No S groups, with greater symptom severity, frequency, and global symptom burdens reported by the IBS-S group. Depression and anxiety scores on the Beck Inventories also were significantly higher in the IBS-S group compared to IBS-No S and healthy controls. Subjective experiences with the low-pressure (25 mm-Hg) rectal balloon distentions trended toward significantly greater discomfort reporting in the IBS-S group ( $p=0.3$ ), but no differences were appreciated across groups with the higher pressure (50-mm Hg) distentions. (Table 1).

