**C. Screening, eligibility, and patient enrollment.** IBS subjects with- and without somatization features will be recruited. To be eligible, subjects will have to be between 18 and 90 years of age (inclusive) and qualify for a diagnosis of irritable bowel syndrome according to the criteria set forth in the Rome III criteria. Comorbid somatization in these IBS subjects will be determined using the Patient Health Questionnaire-15 (PHQ-15). Only subjects with high somatization (PHQ-15  $\geq 10$ ), or low somatization (PHQ-15  $\leq 5$ ), excluding GI symptoms, will be considered for enrollment. Medical history and chart review will be used corroborate the PHQ-15 score, requiring that IBS-S subject  $\geq 2$  additional somatization syndromes, while IBS-No S subjects have a history of  $\leq 1$  non-GI somatization syndrome. Persons are eligible to participate without regard to race or ethnicity. Given sex differences in cerebral responses to noxious stimuli and the greater prevalence of IBS in women, only female participants will be sought in this study. In view of brain hemispheric differences between left- and right-hand dominant individuals, all participants must be right-handed.

*Persons are excluded from participation for having various psychiatric, medical, and other characteristics.*

Psychiatric/cognitive exclusions include any of the following: active suicidal or homicidal ideation or a history of attempted suicide, current excessive alcohol use or other substance abuse disorders, active major depression, anxiety disorder, bipolar depression or any psychotic disorder, unwillingness to be randomized or provide informed consent, inability to communicate with staff or significant cognitive impairment.

Medical and other exclusions include any of the following: renal or hepatic disease or impairment, diabetes, cardiovascular disease, cardiac arrhythmia, cerebrovascular disease, or breastfeeding, pregnant, or imminent intention of pregnancy, history of seizures or primary neurological disorder, head trauma, brain damage, hyper- or hypothyroidism, history or abdominal surgery (other than cholecystectomy/appendectomy), or known structural GI disorder (Crohn's disease, etc.), contraindication to MRI (metallic implant, pacemaker), or rectal balloon distention (e.g., proctitis/colitis).

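### Aim 1 matches on age but leaves age out of every group model, and does not say clearly whether the healthy controls are matched

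*Combined protocol and SAP*

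**What the plan says.** All references are to the combined protocol and SAP.

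- **Age range.** Section 2.C (Screening, eligibility, and patient enrollment) admits IBS subjects "between 18 and 90 years of age (inclusive".
- **Groups.** Specific Aim 1, Design and Methods, enrols "20 IBS-S and 20 age-matched IBS-No S subjects) and 20 healthy controls". The matching label is attached to the IBS-No S group only.
- **Matching rule.** Specific Aim 1, Pitfalls/Limitations, lists age with handedness and sex as causes of activation differences and says that "subjects will be age-matched within 5 years". It neither names nor excludes controls.
- **Aim 1 model.** Analysis/interpretation predicts a group by somatic stimulus "effect on two-way ANOVA analysis of activations within" the predefined regions. The hypothesis sets IBS-S against both other groups: "compared to IBS no-S subjects and healthy controls".
- **Other models.** The additional ANOVAs in Pitfalls/Limitations cover disease duration, symptom severity and psychological features. Data Analysis and Sample Size Calculations describes repeated-measures ANOVAs with three stimulus types. Neither mentions age or the matched set.
- **Pilot.** Table 1 gives mean ages of 47.2 (IBS-S), 45.0 (IBS-No S) and 36.5 (controls), with p = 0.07. The Findings text says: "Subject ages were not significantly different across study groups".

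**The concern.** The plan itself treats age as related to the endpoint and controls it by design. Matching makes the group means more alike than chance would. An analysis that then ignores age keeps the age-related variance in the error term, so its standard error overstates the true uncertainty of the group difference. The test becomes conservative and some of the benefit of matching is lost.

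The control contrast raises a separate question. If controls are not matched, an age difference between IBS subjects and controls passes straight into the estimated group difference, and no planned model would remove it. The pilot shows that such a difference can arise in this setting.

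**Working it through.** **Inputs.** Pilot ages (mean, SD, n = 8 per group), from Table 1: IBS-S 47.2, 8.6; IBS-No S 45.0, 9.7; controls 36.5, 9.2. Aim 1 has 20 per group. The correlation r between age and activation is not in the documents; I take 0.1 to 0.3 as an assumption and add 0.5 as an extreme. Two-sided alpha of 0.05 is also assumed.

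**1. The plan's own figure.** The grand mean age is 42.9.
- Between-group mean square = 8 × [(47.2 − 42.9)² + (45.0 − 42.9)² + (36.5 − 42.9)²] / 2 = 255.4.
- Within-group mean square = (8.6² + 9.7² + 9.2²) / 3 = 84.23, so the within-group SD is 9.18 years.
- F(2, 21) = 255.4 / 84.23 = 3.03, p = 0.0697. The stated 0.07 reproduces.

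**2. The pilot gap to controls.** The pooled IBS mean is (47.2 + 45.0) / 2 = 46.1, so the gap is 46.1 − 36.5 = 9.6 years. The pooled SD for 16 against 8 is 9.02, and the standard error is 9.02 × √(1/16 + 1/8) = 3.90. Then t(22) = 9.6 / 3.90 = 2.46, p = 0.022. IBS-S minus controls is 10.7 years (95% CI 1.2 to 20.2, p = 0.031). IBS-S minus IBS-No S is 2.2 years (p = 0.64).

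**3. Precision when groups are matched but age is ignored.** Standardise activation to SD 1. With near-perfect matching, the variance of the group difference falls by the factor 1 − r², but the unadjusted analysis does not credit this. Its standard error is too large by 1/√(1 − r²). The approximate true type I error is the chance that a t variable on 38 df exceeds 2.024/√(1 − r²) in absolute value.

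| r | SE too large by | Type I error (formula) | Simulated, uniform ages 18–90, matched within 5 years |
|---|---|---|---|
| 0.1 | 0.5% | 0.049 | – |
| 0.2 | 2.1% | 0.046 | 0.045 |
| 0.3 | 4.8% | 0.040 | 0.041 |
| 0.5 | 15.5% | 0.025 | 0.026 |

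**4. Bias in an unadjusted contrast with controls, 20 against 20.** An age gap of g SDs shifts the standardised difference by r × g. The noncentrality is r × g × √(20/2) on 38 df. Two cases:
- The pilot gap recurs: g = 9.6 / 9.18 = 1.05.
- The 5-year rule covers controls and every control is 5 years younger, the worst case the rule allows: g = 5 / 9.2 = 0.54.

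| r | Type I error, pilot gap | Type I error, 5-year worst case |
|---|---|---|
| 0.1 | 0.062 | 0.053 |
| 0.2 | 0.099 | 0.063 |
| 0.3 | 0.162 | 0.079 |
| 0.5 | 0.364 | 0.133 |

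For example, at r = 0.3 with the pilot gap the shift is 0.3 × 1.05 = 0.31 SD and the noncentrality is 0.31 × 3.16 = 0.99. Both columns use the pilot's age SD. A wider spread makes the same gap in years smaller in SD units: uniform ages from 18 to 90 have SD 72/√12 = 20.8, so 5 years is then 0.24 SD.

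**5. Which tests this touches.** Steps 3 and 4 apply to group contrasts of somatic activation. A group by stimulus interaction is tested on within-subject differences between stimuli. An age effect common to all stimuli drops out there, and only an age effect that differs by stimulus remains.

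**The case against.** The limitations text puts age beside handedness and sex, and the right-handed, female-only limits there are not confined to IBS subjects. The Aim 1 design text calls all three arms subject groups. The natural reading is therefore that the 5-year rule includes controls. The pilot methods describe no age matching, so the pilot gap is no forecast for a study that does match. This stands in part: a reader might infer that controls are unmatched and the control contrast biased, but the documents support only that the two passages are unclear. The larger type I figures hold only on the less natural reading.

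Three other inferences also fail.

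- **A material gain in power from adjusting, for example from 0.82 to 0.85–0.89.** The 0.82 belongs to the Aim 2 group by treatment test, and the documents give no correlation between age and activation from which to derive a gain.
- **The same defect in Aim 2.** Its sample is "40 IBS (20 IBS-S and 20 age-matched IBS-No S) subjects", with no controls, and its model compares change from baseline "with IBS Group (IBS-S and IBS-No S) as a between-subject factor". A stable age effect cancels in a change score.
- **A misreported pilot.** The statement that ages did not differ significantly agrees with the three-group p of 0.07. The p of 0.02 is a post hoc pooled contrast. It shows that the non-significant result is weak reassurance with 8 per group, not that the text is wrong.

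It is also fair to say that the loss in the IBS-S against IBS-No S contrast is small and in the conservative direction.

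**Conclusion.** The point holds for Aim 1 and is minor. The plan matches on a variable it regards as related to the endpoint and then omits that variable, and the matched set, from every group model described. For the two IBS groups the consequence is a mildly conservative test, with standard errors about 0.5% to 5% too large at r of 0.1 to 0.3. For controls, the design and limitations texts leave the matching open. If controls are unmatched and the pilot gap recurs, type I error in an unadjusted contrast is about 0.06 to 0.16; if the 5-year rule applies to them, it is at most about 0.05 to 0.08. All these sizes rest on the assumed r, and the control figures also rest on the pilot's age SD. The conclusion that age belongs in the model does not depend on r, because the plan's own text gives the reason for including it.

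**What to change.** 1. In the Aim 1 between-group region-of-interest models, including the contrast with healthy controls, prespecify age as a continuous covariate.
2. Where the group by stimulus interaction is tested, add an age by stimulus term. An age main effect alone does not sharpen or protect that test.
3. Reconcile Specific Aim 1, Design and Methods, with Specific Aim 1, Pitfalls/Limitations: say whether the 5-year rule covers controls and, if so, to which IBS group they are matched.

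The cost is one or a few degrees of freedom and a sentence or two of text. Age is already needed for eligibility and matching, so no new data are required. This point calls for no change to Aim 2 or to the stated power figures.
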